- G. Procedures for monitoring and adjusting lithium levels: Lithium levels will be determined by a Central Lab to ensure consistency as well as prevent accidental unblinding of the local study staff. By contract, the results will be accessible to the MAVERIC data coordinating center within 36 hours of the blood draw, wherein simulated lithium levels for those participants randomized to receive placebo will be calculated. If lithium level results are not available within 72 hours to the local site, consultation with the Central psychiatrist / CSP590 Safety Officer is required.

The MAVERIC data coordinating center will provide the lithium levels (actual level for participants in active group and simulated level for participants in placebo group) to the Site Physician and the Central Psychiatrist/Safety Officer. The Site Physician, after consultation with the Central Psychiatrist/Safety Officer as needed, will make the final dose adjustments and document the dose, using the provided lithium level and all the clinical information available.

Simulated levels will be calculated as outlined in Section XIII.

The planning group considered an alternative proposal in which all dose adjustments would be done by the Central Psychiatrist/Safety Officer on the basis of lithium levels from the laboratory and clinical information from the study site. In this approach, the Site Physician would execute the recommendation by prescribing the recommended dose unless there was a compelling clinical reason to modify it. The principle advantage of this might be less variability between sites in decision-making about dose adjustments. However, the planning consultants felt this process for titration of the medication would be complicated and cumbersome. Specifically, there was a consensus that it would limit the study's ability to respond to what might be subtle indicators about minor side effects or discomforts with the study medication. Accordingly, there were concerns that it might increase the risk of more significant side effects or dropouts.

Other designs were considered including:

1. A randomized controlled trial (RCT) comparing active treatments: This possibility was rejected because, other than lithium, there is no justification for use of any other medication as adjunctive treatment for patients with depression or bipolar disorder.

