- 1) Calculate a plasma level for the current dose using the method of Abou-Auda (2008).

- 2) Adjust the plasma upwards if there are reports of side effects, and downward, if there are reports of non-adherence; these adjustments are intended to ensure that the simulated plasma levels appear plausible and realistic in light of the patient's clinical status.
- 3) Multiply the adjusted value by a random factor. This is necessary to ensure that there is a realistic degree of week to week variability for simulated plasma levels and that the reported values cannot signal the Research Team at the study site about whether the plasma levels are real or simulated.

During the course of the study, the study biostatistician will periodically compare the distributions of real and simulated plasmas levels to ensure that there are no significant differences. Should there be trends suggesting they are diverging, the biostatistician will work with the MAVERIC data coordinating center to revise the parameters for calculating simulated measures.

All participants will have flags in their VA electronic medical records in accordance with local policy. This study falls under the 1200.05 2012 version, however, we recommend that the flags state that the participants are enrolled in a research study and any medication changes or drug level testing be done only after consulting the Site Physician. The amount of information provided within the flags may vary by site according to local policies and procedures.

The processes for dispensing medication from a VA pharmacy or by mail will be developed for each patient, depending upon whether patients are inpatients (at the start of the study) or outpatients, and whether or not they have convenient access to a VA facility. Medications will be dispensed in blister cards containing medication for two weeks. Some participants may be dispensed one week of medication at a time if the investigator determines this is more appropriate for the safety of the participant. Participants will be asked to return unused blister cards at the next study visit to perform tablet counts to assess adherence.

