3.2. Description of the Intervention Strategy

Eligible patients who consent to participate will be randomized to receive Lithium or placebo. Initial dosage will be 600 mg /day of lithium (or matching placebo), to be titrated to achieve serum lithium level of 0.6 to 0.8 meq/liter. Mock serum lithium level for placebo patients will be calculated using Therapeutic Drug Monitoring method (Yukawa, 1993) based on age, weight, serum creatinine level, adherence, and side-effects. Titration visits will occur at intervals of 5-7 days over 3 months, with maximum allowed dosage not to exceed 1500mg.

Once the target serum lithium level has been reached the patient will be on steady state maintenance phase for the rest of the study with active participation and intervention terminating at 12 months after randomization.

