5.1. Secondary Objective

This trial has 5 secondary objects, which are described below. Analyses for these objectives are exploratory in nature and as such, they are not statistically powered for formal hypothesis testing. These objectives are to:

- 1) explore the effectiveness of lithium augmentation of enhanced suicide prevention management in preventing separately:
 - a. all-cause mortality
 - b. impulsive suicide reattempts
 - c. non-impulsive suicide reattempt
 - d. non-suicidal self-directed violence
- 2) explore heterogeneity of response to treatment subgroups including:
 - a. categories of age, race/ethnicity, and gender
 - b. diagnosis of depression vs. bipolar disorder
 - c. impulsive index attempt vs. non-impulsive index attempt
 - d. substance use vs. absence of substance use
 - e. individuals with and without trait impulsivity
 - f. individuals with and without trait aggression
 - g. subjects who have vs. have not received evidence based psychotherapies
- 3) explore the effect of lithium augmentation of enhanced suicide prevention management on total occurrence of all event types and cumulative occurrence of individual event type as follows:
 - a. all suicide attempts
 - b. all hospitalizations for prevention of suicide attempts
 - c. all self-directed violence
 - d. all emergency department visits

- 4) explore longitudinally the effect of lithium augmentation of enhanced suicide prevention management on symptoms of bipolar disorder and depression and suicidal ideation
- 5) explore mediators of the effect of lithium augmentation on prevention of suicide reattempt, specifically improved control of symptoms and lithium plasma levels

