5.2. Secondary Endpoints

There are multiple secondary endpoints being considered for the study where endpoint events for secondary objectives #1, 2, and 5 will be assessed as time to event outcomes, endpoint events for secondary objective # 3 will be assessed as count data, and endpoint events for Secondary Objective #4 will be evaluated as a binary outcome.

For Secondary Objective #1, Time from randomization to death from any cause will be analyzed. Additionally, self-directed violence as described in section 4.2 will be classified further as either impulsive or non-impulsive attempt based on Beck Suicide Intent Scale, (Question#15 on CRF-Form S8), and will be analyzed separately. Lastly, non-suicidal self-directed violence behavior defined as the primary endpoint without the death from suicide will be considered as a separate outcome.

For Secondary Objective #2 which evaluates efficacy in different subgroups, the primary endpoint as described in section 4.2 will be analyzed.

The endpoint for Secondary Objective #3 considers all components of self-directed violence as described in section 4.2. Therefore, a combined total of all episodes of all components of the primary outcome will be an endpoint, and total counts of each component, in addition to all emergency department visits will be separate endpoints.

For Secondary Objective #4, dependent variables being considered longitudinally include (1) presence or absence of symptoms, and (2) presence or absence of suicidal ideation. Presence or absence of symptoms will be derived by the Internal State Scale (CRF-Form B8), and presence or absence of suicidal ideation will be derived from the Columbia Follow Up Questionnaire (CRF-Form B6).

Lastly, for Secondary Objective #5, the endpoint event will be the same as the primary endpoint described in section 4.2.

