Secondary objective#5 will be evaluated by Cox Proportional Hazard regression analysis method comparing regression coefficients for treatment effect in the models with and without the mediator (Sobel, 1982). Additionally, we will explore bootstrapping methods to evaluate mediators as described in MacKinnon et al.(2002), Preacher & Hayes (2008), and MacKinnon (2003).

6. Analysis Plan for Tertiary Objectives

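### Lithium plasma level is planned as a mediator, but it measures exposure to the assigned drug, and the placebo value to be used is not specified

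*SAP*

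**What the plan says.** SAP 5.1 lists as its fifth secondary objective the exploration of mediators, "specifically improved control of symptoms and lithium plasma levels". The protocol names the same two under objective (e) of the Secondary Data Analysis Plan (Section VII). SAP 5.3 gives the method: Cox regression, "comparing regression coefficients for treatment effect in the models with and without the mediator", with bootstrap methods also to be explored. SAP 5.2 fixes the outcome: "for Secondary Objective #5, the endpoint event will be the same as the primary endpoint". SAP 5.1 calls all secondary analyses exploratory and unpowered.

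Placebo patients should have almost no lithium in the blood. Use within six months is an exclusion (Protocol V), and a participant whose provider finds lithium essential is withdrawn (Protocol XIII). To protect the blind, they are given invented values. Protocol VIII.G says that "simulated lithium levels for those participants randomized to receive placebo will be calculated"; SAP 3.2 says "Mock serum lithium level for placebo patients will be calculated using Therapeutic Drug Monitoring method". Under Protocol XIII the study biostatistician will periodically "compare the distributions of real and simulated plasmas levels to ensure that there are no significant differences", and the simulation parameters are revised if the two drift apart.

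Neither document says whether a placebo patient enters the mediation model with zero, a measured value or the simulated value. Neither says how a level that changes over time, or is no longer measured, is handled. In Protocol Table 7 (participants off study medication) the lithium-level row has no visit marked.

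**The concern.** A mediator should be a step between treatment and outcome that can be separated from treatment. Plasma level is the delivered treatment itself. If lithium works pharmacologically at all, it works through lithium in the blood, so a proportion mediated by level says little about mechanism.

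The arithmetic of the planned comparison adds to this. With placebo at zero, the treatment coefficient in the model that includes level contrasts a lithium-arm patient at level zero with a placebo patient. If everyone takes the drug, that is an extrapolation: at the mean and SD cited in Protocol XIII, zero lies 0.624/0.134 = 4.7 SDs below the mean. If some lithium patients are at zero, the contrast sets people who stopped or never took the drug against the whole placebo arm, and randomisation no longer protects it. With simulated placebo values, the arms are matched on level deliberately, so there is no arm-to-level path left to find.

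At stake is a secondary objective and the planned paper on mediators and moderators (Protocol XX, item 7). A reader could take either an unstable proportion mediated or a null produced by the simulated levels as evidence about how lithium works.

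**Working it through.** **Design figures.** The documents give no figure for the mediation analysis, so the check uses the primary design (SAP 10). Events: 745 × (0.15 + 0.0945) = 182. Hazard ratio: ln(1 − 0.0945)/ln(1 − 0.15) = 0.611. Power with 182 events and HR 0.61 is 91.5% (Schoenfeld) or 90.5% (Freedman) at two-sided 0.05, and 91.3% or 90.2% at 0.048. The stated 90% reproduces.

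**How far arm determines true level.** Placebo level is taken as 0. In the lithium arm a share q sits at 0 and the rest have mean μ and SD σ. With 1:1 allocation:

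- lithium-arm mean m = (1 − q)μ; lithium-arm variance w = (1 − q)σ² + q(1 − q)μ²
- R² = 0.25m² / (0.25m² + 0.5w); variance inflation VIF = 1/(1 − R²); standard-error factor = √VIF

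Inputs: μ = 0.624 and σ = 0.134 mEq/L come from an observational study cited in Protocol XIII and are an assumption for this trial. The values q = 0.15 and 0.20 are the two non-adherence allowances in Protocol VII; placing those patients at level zero is also an assumption.

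| q | 0.25m² | 0.5w | R² | VIF | SE factor |
|---|---|---|---|---|---|
| 0 | 0.0973 | 0.0090 | 0.916 | 11.8 | 3.4 |
| 0.15 | 0.0703 | 0.0325 | 0.684 | 3.2 | 1.8 |
| 0.20 | 0.0623 | 0.0383 | 0.619 | 2.6 | 1.6 |

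Other assumptions move this. Mean 0.7, SD 0.1, q = 0 gives R² 0.961 and VIF 25.5. Mean 0.5, SD 0.25, q = 0 gives 0.0625/(0.0625 + 0.03125) = 0.667 and VIF 3.0. The cited mean and SD with 40% at zero give 0.402 and 1.7.

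**The planned comparison, simulated.** N = 1490, 15% placebo event rate, HR 0.61, one year, no dropout, one fixed level per patient. Proportion mediated = 1 − (treatment coefficient with level)/(treatment coefficient without level). No confounding in this table.

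| Placebo value | q | True path | Runs | Median | 5th to 95th percentile |
|---|---|---|---|---|---|
| zero | 0 | all through level | 300 | 1.05 | −1.10 to 4.03 |
| zero | 0 | none through level | 300 | 0.05 | −1.95 to 2.12 |
| zero | 0.20 | all through level | 120 | 1.12 | 0.34 to 2.28 |
| zero | 0.20 | none through level | 120 | 0.02 | −0.97 to 0.83 |
| simulated | 0 | all through level | 120 | 0.00 | −0.02 to 0.02 |
| simulated | 0.20 | all through level | 120 | 0.00 | −0.03 to 0.05 |

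In the first row the standard error of the treatment coefficient rises from 0.15 to 0.56 when level is added.

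**Confounding by adherence.** Let unmeasured risk raise both the log-odds of non-adherence (by 1 per SD, with 20% non-adherence at average risk) and the log hazard (by 0.5 per SD). These strengths are assumed. With true levels and no lithium effect at all, level is significant at 0.05 in 53% of 120 runs. With an effect wholly through level, the median proportion mediated moves from 1.12 to 1.76.

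**The case against.** Four points on the other side have force.

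- A reader might infer that level is almost fully fixed by arm and is also simulated on placebo. Those are two exclusive choices: with simulated values, arm explains about none of the variance. Even with true levels, almost fully fits only patients who take the drug. Under the protocol's own 15% to 20% non-adherence the share is 62% to 68%. Lower collinearity does not rescue the analysis, because the added variation is self-selected.
- A reader might infer that the SAP intends to analyse simulated levels. No passage says so. They are described for blinding and titration, and SAP 3.4 uses serum level for adherence in the lithium group only. What stands is that objective 5 is silent.
- A reader might say that the split of the effect is arbitrary, or that the planned model cannot address level and protection at all. Without confounding, the simulated medians sit near the truth; the fault there is imprecision, which bootstrap intervals would show. With placebo at zero the level coefficient already comes only from the lithium arm, so it is close to the exposure-response contrast recommended below and shares its confounding. What fails is calling the change in the treatment coefficient mediation.
- The planned paper on level and repeated attempts (Protocol XX, item 8) is listed apart from the mediator paper and need not depend on this model.

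Exploratory status excuses low power. It does not excuse a quantity that has no mediation reading under one choice and is zero by construction under the other. One sentence setting placebo to zero would remove the second problem but not the first.

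**Conclusion.** The concern holds in this form. Plasma level is exposure to the assigned drug, and the placebo value is unspecified. With true levels, arm explains roughly 62% to 92% of its variance (VIF 2.6 to 11.8), and the mediation estimate is imprecise and confounded by adherence. With full adherence, opposite truths give largely overlapping results; with 20% at zero the ranges still overlap between 0.34 and 0.83. With simulated levels, the estimate is about zero whatever the truth.

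The ranges rest on a borrowed mean and SD, on non-adherers sitting at zero, and on an assumed strength of confounding. The structural conclusion does not depend on those figures. The symptom mediator and the primary analysis are unaffected. This is a minor point.

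**What to change.** 1. Remove plasma level from the mediators in Protocol Section VII objective (e) and SAP 5.1 objective 5. Keep control of symptoms.
2. State in the SAP that simulated or mock levels enter no efficacy analysis.
3. Add an exploratory exposure-response analysis in the lithium arm: a Cox model for the primary endpoint with time-updated measured level, adjusted for baseline risk factors and for predictors of adherence and clearance (age, weight and creatinine are already collected). Specify how level is carried between visits and after study medication stops. Label it observational.
4. Add dose as a covariate only in a sensitivity analysis. Dose is titrated to level (Protocol XIII), so conditioning on it leaves mainly clearance and adherence.

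The cost is one reworded objective in each document and one substituted exploratory model. Sample size and data collection do not change. The replacement is still non-randomised and will not prove a level-response effect.

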5.2. Secondary Endpoints

There are multiple secondary endpoints being considered for the study where endpoint events for secondary objectives #1, 2, and 5 will be assessed as time to event outcomes, endpoint events for secondary objective # 3 will be assessed as count data, and endpoint events for Secondary Objective #4 will be evaluated as a binary outcome.

For Secondary Objective #1, Time from randomization to death from any cause will be analyzed. Additionally, self-directed violence as described in section 4.2 will be classified further as either impulsive or non-impulsive attempt based on Beck Suicide Intent Scale, (Question#15 on CRF-Form S8), and will be analyzed separately. Lastly, non-suicidal self-directed violence behavior defined as the primary endpoint without the death from suicide will be considered as a separate outcome.

For Secondary Objective #2 which evaluates efficacy in different subgroups, the primary endpoint as described in section 4.2 will be analyzed.

The endpoint for Secondary Objective #3 considers all components of self-directed violence as described in section 4.2. Therefore, a combined total of all episodes of all components of the primary outcome will be an endpoint, and total counts of each component, in addition to all emergency department visits will be separate endpoints.

For Secondary Objective #4, dependent variables being considered longitudinally include (1) presence or absence of symptoms, and (2) presence or absence of suicidal ideation. Presence or absence of symptoms will be derived by the Internal State Scale (CRF-Form B8), and presence or absence of suicidal ideation will be derived from the Columbia Follow Up Questionnaire (CRF-Form B6).

Lastly, for Secondary Objective #5, the endpoint event will be the same as the primary endpoint described in section 4.2.

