This study will be implemented in FY2015, when the mental health field in VA and the remainder of the United States is transitioning from use of DSM-IV-TR (American Psychiatric Association, 2000) to DSM-5 (American Psychiatric Association, 2013) to guide the diagnosis of mental disorders. To maximize compatibility of research diagnoses with the clinical diagnoses available through VA electronic medical records, inclusion and exclusion criteria for this study will remain based on DSM-IV-TR. However, procedures for diagnosis and assessment of key disorders will be modified, as needed, to allow characterization of patients in terms of both DSM-IV-TR and DSM-5 diagnostic criteria.

For inclusion in this study, suicide attempts must meet the definition for a suicide attempt based on the CDC's document, "Self Directed Violence and Surveillance: Uniform Definitions and Recommended Data Elements" (Crosby et al., 2011). This system was developed in collaboration with VA, and was subsequently adopted by both DoD and VA as a means for defining attempts on the basis of behavior, reports or judgments about intent, and context. According to the CDC definition, an attempt is, "A non-fatal self-directed potentially injurious behavior with any intent to die as a result of the behavior. A suicide attempt may or may not

result in injury.” It includes suicidal self directed violence, “Behavior that is self-directed and deliberately results in injury or the potential for injury to oneself. There is evidence, whether implicit or explicit, of suicidal intent.” The CDC definition includes interrupted self-directed violence-by self or by other.

“By self” (in some documents, termed “abortive” suicidal behavior) means a person takes steps to injure self but is stopped by self prior to fatal injury,” when there is implicit or explicit evidence of suicidal intent. “By other” means a person takes steps to injure self but is stopped by another person prior to fatal injury. The interruption can occur at any point during the act such as after the initial thought or after onset of behavior.

Finally, the inclusion criteria go beyond the CDC definition to include cases where patients were hospitalized to prevent suicide. To summarize, the goal in defining the inclusion criteria related to suicidal self-directed violence is to ensure that they are representative of those clinically considered to have attempted suicide or have been at imminent risk.

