The starting dose of lithium will be 300 mg. Subjects on antihypertensive medications will need to be on a stable dose, defined as being on the same dose of antihypertensive medication for at least one week while achieving adequate blood pressure control. Monitoring will be intensified with lithium levels obtained monthly throughout the study once they are at steady state. Patients starting diuretic (amiloride) and ACE inhibitors/AR blockers may continue study medication at a reduced dose and increased monitoring as described in “Ongoing Dose Adjustments” in Section XIII).

Patients taking haloperidol are excluded because there are concerns of specific interactions with lithium in the central nervous system. Patients taking clozapine are excluded because its indications, treatment-resistant schizophrenia and reducing recurrent suicidal behavior in schizophrenia or schizoaffective disorders, are not compatible with the inclusion criteria.

VI. STUDY MEASURES

The baseline assessment will collect basic information including race, ethnicity, educational attainment, period of military service, combat exposure, and marital status. Tables 1 and 6 summarize the other data to be collected, their source, and the estimated time required of the participant.

Primary Outcome

The primary outcome will be time to the first repeated episode of suicidal self directed violence including (non-fatal) suicide attempts and deaths from suicide over the one year follow-up period. Interrupted attempts and hospitalizations specifically for the prevention of suicide will be considered equivalent to attempts. To minimize variability and bias in identifying episodes of suicidal self-directed violence, the Outcomes Adjudication Committee will review all potential outcome events, and make final determinations about which should be considered.

The nomenclature and definitions for suicide-related behaviors will follow CDC definitions (Crosby et al., 2011). By definition, an attempt must be accompanied by a wish to die, either reported by the patient, or inferred on the basis of his or her behavior. Repeated suicide attempts are clinically significant outcomes and a proxy for death from suicide.

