The study will utilize all available sources of information about repeated suicide attempts including the medical record and VA-Suicide Prevention and Application Network (SPAN) data. As proposed in the draft FDA guidelines for clinical trials in suicide (*FDA Suicidal Ideation and Behavior Draft Guidance*, 2012), the study will utilize the Columbia Suicide Severity Rating Scale (CSSRS; Posner et al., 2011), supplemented with additional information about preparatory behavior, interrupted attempts, and other forms of self-directed violence (e.g., whether the event was a suicide attempt, an event of undetermined intent, or non-suicidal self-directed violence) to align the CSSRS with the recently adopted CDC classification system (Crosby et al., 2011). The need for additional information to allow cross-walking between the Columbia and CDC approaches has been documented by the Matarazzo et al. (2013).

For reports of suicide attempts, self-report data from the CSSRS will be supplemented with information from the Suicide Intent Scale (Beck et al., 1974) to allow further characterization of attempts, and to distinguish impulsive from non-impulsive attempts (Spokas et al., 2012). For these analyses, attempts will be considered to be impulsive when the patient reports no premeditation on the Suicide Intent Scale.

Adjudication of Primary Outcome

An Outcomes Adjudication Committee will review redacted documents of possible attempts and related events, analogous to the procedures used in the InterSept study of clozapine for preventing suicide-related behaviors in patients with schizophrenia (Meltzer et al., 2003). Reports using a modification of the template of Brown and Holloway (Brown & Holloway, 2005) for use in clinical trials of Cognitive Therapy for Suicide Prevention (Brown et al., 2005) will be submitted to the Outcomes Adjudication Committee for each episode considered to be a possible suicide attempt, an interrupted attempt, another form of self-directed violence, a death from suicide, or an accident.

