In addition to repeated episodes of suicidal self-directed violence, the study will obtain data on a number of secondary outcomes within the 12 month follow up period. These will go beyond the time to the first outcome event to include the total numbers of suicide attempts, interrupted attempts, hospitalizations for the prevention of suicide, emergency department visits, non-suicidal self-directed violent behaviors, and deaths from suicide, unnatural deaths, and all-causes. To support exploratory analyses on subtypes of suicide attempts, the study will obtain data on impulsive and non-impulsive attempts.

Following the total number of suicide attempts and time to the first attempt will allow comparison of our findings with other studies that used rates of attempts as an outcome. Following the impact of the study treatment on other forms of self-directed violence will allow us to explore the specificity of the observed treatment effects. The proposal to evaluate treatment effects on all unnatural deaths and on all-cause mortality follows from concerns that deaths from other causes in patients who have survived suicide attempts may represent suicide-equivalents or cases misclassified by medical examiners or coroners. However, we recognize that the observed rates of all-cause of mortality in persons who have attempted suicide are lower than reattempt rates, and, therefore, the study would not be powered to detect a treatment effect on overall mortality. Finally, exploratory analyses on impulsive versus non-impulsive attempts, defined on the basis of reports of the absence or presence of premeditation on the Suicide Intent Scale, may provide further insights into whether any observed effects of lithium could be related to a decrease in impulsive behaviors.

Covariates

Measures of potential effect modifiers will include traits of impulsivity and aggression. Measures of potential mediators will include symptoms of the patients' affective disorders (including suicidal ideation).

VII. BIOSTATISTICAL CONSIDERATIONS

Overview

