4.2. Primary Endpoint

The primary outcome measure is time from randomization for treatment allocation to the first episode of suicidal self-directed violence assessed over one year follow up period. Episode of suicidal self-directed violence include (1) non-fatal suicide attempts, (2) interrupted attempts, (3) hospitalizations specifically to prevent suicide, and (4) deaths from suicide. All potential primary endpoints identified via CRFform data (mostly through the serious adverse event reporting or Columbia Follow Up form), will be evaluated by two independent adjudicators. If the adjudicators do not agree in deciding the event to be (or not to be) the primary endpoint event, then a third adjudicator will evaluate the same information and serve as a tie-breaker.

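### The SAP's non-suicidal self-directed violence endpoint is the primary endpoint minus suicide deaths, so it nearly repeats the primary and contains no non-suicidal events

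*SAP*

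**What the plan says.** SAP 5.1 gives four outcomes under secondary objective 1. The fourth (1d) is "non-suicidal self-directed violence". SAP 5.2 supplies the working definition: "non-suicidal self-directed violence behavior defined as the primary endpoint without the death from suicide will be considered as a separate outcome". SAP 5.3 then assigns every objective 1 endpoint a log-rank test and a Cox model.

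The primary endpoint being modified is in SAP 4.2: "Episode of suicidal self-directed violence include (1) non-fatal suicide attempts, (2) interrupted attempts, (3) hospitalizations specifically to prevent suicide, and (4) deaths from suicide".

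The protocol uses the term differently. In section VI, Primary Outcome, the Columbia scale is supplemented so that it can record "whether the event was a suicide attempt, an event of undetermined intent, or non-suicidal self-directed violence", which makes these separate classes. Section VI, Other Outcomes, lists non-suicidal self-directed violent behaviours as an item distinct from attempts, interrupted attempts and preventive hospitalisations. It adds that following other forms of self-directed violence "will allow us to explore the specificity of the observed treatment effects".

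**The concern.** The name and the definition in SAP 5.2 describe opposite sets of events. The name says there was no suicidal intent. The definition takes a composite made up only of suicidal events and drops the fatal ones. It appears that non-suicidal was read as non-fatal.

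Two things follow. First, the analysis for 1d will closely track the primary result and says almost nothing new. Second, it may be read as evidence about non-suicidal self-harm. If the primary is positive, 1d will probably look positive too and will suggest that lithium acts on self-harm in general, when no such event was analysed. If the primary is null, a reader may infer no effect on a behaviour that was never examined. Either way, the protocol's question about specificity goes unanswered.

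**Working it through.** **Step 1: what the definition leaves.** Taking the fourth component out of SAP 4.2 leaves three:

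- Non-fatal suicide attempts. Protocol VI, Primary Outcome, says "an attempt must be accompanied by a wish to die".
- Interrupted attempts. In the rationale to the inclusion criteria (protocol V), self-interrupted acts count "when there is implicit or explicit evidence of suicidal intent".
- Hospitalisations specifically to prevent suicide, which are suicidal by their stated purpose.

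A subset of a suicidal composite cannot contain a non-suicidal event, so the number of non-suicidal events counted is 0 by construction.

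**Step 2: is the gap filled elsewhere?** SAP 5.1 objective 3c refers to all self-directed violence. SAP 5.2, however, confines objective 3 to the section 4.2 components plus emergency department visits. The impulsive and non-impulsive endpoints are also built from section 4.2. No SAP endpoint covers non-suicidal self-directed violence.

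**Step 3: reproduce the plan's event count.** Inputs (SAP section 10): 745 evaluable per arm, one-year rates of 15% and 9.45%, final two-sided alpha 0.048.

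- Events = 745 × (0.15 + 0.0945) = 182.2 (plan: 182).
- Hazard ratio = ln(1 − 0.0945) / ln(1 − 0.15) = 0.611 (plan: 0.61).
- Power at alpha 0.048 = 90.0% by Freedman's formula and 91.1% by Schoenfeld's (plan: 90%).

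The plan's figures reproduce.

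**Step 4: overlap with the primary.** Protocol section II gives one-year suicide death rates among VA attempt survivors of 0.44%, about 0.5%, 0.54% and 0.80%. Assume equal rates in both arms and that every suicide death is a first primary event. Then deaths = 1490 × rate, and overlap = (182.2 − deaths) / 182.2.

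| Suicide death rate | Deaths in 1490 | Events left | Overlap | Overlap if deaths are 37% lower on lithium |
|---|---|---|---|---|
| 0.44% | 6.6 | 175.6 | 96.4% | 97.1% |
| 0.5% | 7.5 | 174.7 | 95.9% | 96.7% |
| 0.54% | 8.0 | 174.1 | 95.6% | 96.4% |
| 0.80% | 11.9 | 170.2 | 93.5% | 94.7% |

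The last column uses deaths = 745 × rate × (1 + 0.63). In the placebo arm alone at 0.5%, the overlap is (15 − 0.5) / 15 = 96.7%. At the community rate of about 2%, which the protocol describes as higher than in VA, the overlap is still 83.6% (equal rates) or 86.7% (37% lower on lithium).

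Treating every suicide death as a first event understates the overlap. A participant who dies by suicide after an earlier non-fatal event already has that earlier event as the first primary event.

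**Step 5: what cannot be computed.** The documents give no rate for non-suicidal self-directed violence, so the expected count under a corrected definition is unknown.

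**The case against.** The best defence is that this is a naming slip in an exploratory item. SAP 5.1 describes the secondary objectives as exploratory and not powered for formal testing. The minimum content of the final report in SAP section 11 does not include this endpoint. If the authors meant non-fatal events, the analysis is coherent and only the label is wrong. The protocol is also looser than it might be: item (a)4 of its Secondary Data Analysis Plan (section VII) says only self-directed violence, without the qualifier. Its Other Outcomes section treats non-suicidal behaviours as total numbers rather than as a time to first event.

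A further point concerns the remedy. The protocol has the adjudication committee sort events into the four primary types or other types, and SAP 4.2 describes only a decision on whether an event is a primary endpoint. Neither names a non-suicidal class, so an adjudicated classification cannot be taken for granted.

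Most of this bears on the weight of the point or the detail of the fix. Exploratory status limits the consequence but does not make a definition match its name. The looser wording in protocol VII does not help the SAP, which itself wrote non-suicidal in both 5.1 and 5.2. Protocol section VI settles the intended meaning. Even if non-fatal was meant, the protocol's non-suicidal outcome then has no analysis at all. The point about adjudication stands, and the fix should name its data source.

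**Conclusion.** The concern holds. As written, objective 1d analyses non-fatal suicidal events under the name of non-suicidal ones. It retains roughly 94% to 96% of the primary events with both arms pooled (97% in the placebo arm at 0.5% suicide deaths) and counts none of the events it is named for. The overlap figures rest on the plan's own event rates and the protocol's VA suicide death rates, with equal death rates by arm and each suicide death counted as a first event. The zero rests on the definition alone and needs no assumption.

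The SAP should be corrected, but the effect is confined to one exploratory secondary endpoint. The primary analysis, type I error and sample size do not change.

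**What to change.** In SAP 5.2, define the endpoint for objective 1d as time from randomisation to the first event of deliberate self-directed injurious behaviour without evidence of suicidal intent. State:

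- the source of the classification: the supplemented Columbia scale, with adjudication where the committee's record separates this class from other non-primary events;
- how events of undetermined intent are handled, for example left out of the main analysis and added in a sensitivity analysis.

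If the current event set is also of interest, keep it as a separate endpoint called non-fatal suicidal self-directed violence. Because protocol VI lists non-suicidal behaviours among total counts, consider adding a matching count under objective 3.

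The cost is SAP wording plus a check of what the adjudication record holds. The supplemented scale is already meant to record the class, and protocol VI already has sites send reports of other self-directed violence to the committee, so no new data collection is needed. Make the change before treatment assignments are available to those who write the definition.
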